#### 6.3.5 Reporting of serious adverse events

All SAEs have to be reported, whether or not considered causally related to the IP, or to the study procedure(s). All SAEs will be recorded in the eCRF.

If any SAE occurs in the course of the study, then investigators or other study site personnel must inform appropriate AstraZeneca representatives within 1 day, ie, immediately, but **no** later than the end of the next business day of when he or she becomes aware of it.

The designated AstraZeneca representative works with the investigator to ensure that all the necessary information is provided to the AstraZeneca Patient Safety data entry site within **1 calendar day** of initial receipt for fatal and life-threatening events **and within 5 calendar days** of initial receipt for all other SAEs.

For fatal or life-threatening AEs where important or relevant information is missing, active follow-up is undertaken immediately. Investigators or other study site personnel must inform AstraZeneca representatives of any follow-up information on a previously reported SAE within 1 calendar day, ie, immediately, but **no later than the end of the next business day** of when he or she becomes aware of it.

If the eDC system is not available, then the investigator or the other study site personnel reports an SAE to the appropriate AstraZeneca representative by telephone.

The AstraZeneca representative will advise the investigator/study site personnel how to proceed.

Refer to the study-specific Safety Handling Plan for details on SAE reporting using the eDC system.

#### 6.3.6 Daily opioid dose

Opioid doses will be recorded for each patient and the daily opioid dose in morphine equivalents will be calculated. Daily maintenance opioid dose and breakthrough opioid pain medication will be recorded on eCRFs at study visits. A home diary will be assigned to each patient to facilitate collection of breakthrough opioid pain usage.

#### 6.3.7 Bisacodyl use

Bisacodyl use will be recorded for each patient on bisacodyl accountability eCRFs at study visits.

### 6.3.8 NRS

Pain intensity is commonly evaluated via single-item measures that require patients to provide a quantifiable categorical and/or numerical rating of their pain. The most evaluated measures of pain intensity include NRS and visual analogue scales; both have been shown to demonstrate excellent psychometric characteristics across a wide range of clinical trial environments. The 11-point NRS has been recommended as the preferred response format for use in clinical trials (Dworkin et al 2005). The NRS rates pain from 0 (no pain) to 10 (worst pain imaginable). Changes in this scale should generally not be reported as AEs unless standard criteria for AE reporting are otherwise met.

Patients will be asked to complete the NRS at study visits indicating their average pain during the 7 days prior to the visit. The NRS will be completed by patients on the SitePad device provided at the study center. Study staff will provide initial training to patients and will log patients in. Patients are to fill out the questionnaire in a quiet area, without any help from family, friends, or study staff. With the exception of Visit 1, where some interaction with staff will be necessary in order to ensure that enrollment criteria have been met, patients are to fill out the NRS prior to any interventions or discussions regarding their OIC with the study staff or the investigator.

### 6.3.9 Modified Himmelsbach Scale

Patients are rated by examination for symptoms of opioid withdrawal using the modified Himmelsbach scale. The modified Himmelsbach scale will be administered by a clinician at the study site. Patients will be rated with respect to the following symptoms as observed at the time of the assessment: yawning, lacrimation, rhinorrhea, perspiration, tremor, mydriasis, piloerection, and restlessness. The signs will be quantified on a scale of 0 to 3, with 0=none, 1=mild, 2=moderate, 3=severe. (Himmelsbach 1941; Culpepper-Morgan et al 1992, Webster et al 2008). To ensure adequate inter-rater agreement, raters will undergo training on proper scoring using the modified Himmelsbach scale and will receive certification provided by Bracket Global. The modified Himmelsbach scale will be administered at Visit 1 (enrollment - data obtained at the Visit 8 of previous study D3820C00004) and Visit 4 (Week 12). Changes in this scale should generally not be reported as AEs unless standard criteria for AE reporting are otherwise met.

#### 6.3.10 Laboratory safety assessment

Laboratory assessments will be conducted at a central laboratory. Blood and urine samples for determination of clinical chemistry, hematology, and U/A will be taken at the times indicated in the Study Plan (Table 1).

The following clinical laboratory tests (chemistry, hematology, and U/A shown in Table 4) will be performed as specified in the Study Plan.

#### Table 4Laboratory assessments

Hematology	Clinical Chemistry	Urinalysis f	
B-Hb	S-Albumin	U-Glucose	
B-Hematocrit	S-ALT a	U-Blood	
B-Erythrocyte count	S-ALP	U-Protein	
B-Leukocyte count	S-AST a	U-Leukocytes	
B-Leukocyte differential count	S-Bicarbonate	U-Pregnancy test (WOCBP) d	
B-Neutrophils (Absolute and %)	S-Bilirubin, Direct b		
B-Lymphocytes (Absolute and %)	S-Bilirubin, Indirect b		
B-Monocytes (Absolute and %)	S-Bilirubin, Total	Urine Drug Screen	
B-Eosinophils (Absolute and %)	BUN	barbiturates	
B-Basophils (Absolute and %)	S-Ca	benzodiazepines	
B-Platelet count	S-Creatinine	cannabinoids	
B- MCV	S-Chloride	cocaine	
B- MCH	S-Glucose	methadone	
B- MCHC	S-Potassium	methaqualone opiates	
B- RDW	S-Sodium Total cholesterol c TSH S-Pregnancy test d		
		phencyclidine	
		propoxyphene	
		amphetamine	
		tetrahydrocannabinol	
	Caserulation		

#### Coagulation

INRe

ALP alkaline phosphatase; ALT alanine aminotransferase; AST aspartate aminotransferase; B whole blood; BUN blood urea nitrogen; Ca calcium; Hb haemoglobin; INR international normalized ratio; MCH mean corpuscular haemoglobin; MCHC mean corpuscular haemoglobin concentration; MCV mean corpuscular volume; PT prothrombin time; RDW red blood cell distribution width; S serum; TSH Thyroid stimulating hormone; U urine; WOCBP women of childbearing potential.

A separate protocol is outlined regarding additional laboratory tests for elevated liver transaminases (see Section 6.3.10.2).

b Direct and Indirect Bilirubin will be assessed only if the Total Bilirubin value is outside the normal reference range.

c Total cholesterol will be assessed at enrollment (Visit 1) and Week 12 (Visit 4/end of treatment).

A urine pregnancy test will be performed at enrollment (Visit 1); if the urine pregnancy test is positive, it is to be

followed up with a serum pregnancy test. A serum pregnancy test will be performed at Visit 4 and Visit 5.
e INR is to be assessed during the study if patients meet criteria for significant elevation in liver transaminases (See

Section 6.3.10.2).

f If urinalysis is positive for blood, protein, or glucose, microscopic testing is to be conducted.

Serum chemistry and hematology tests will be performed on all patients at Visit 1 (enrollment - data obtained at the Visit 8 of previous study D3820C00004), Visit 4 (Week 12), and Visit 5 (Week 14, follow-up). Total cholesterol will be assessed at Visit 1 (enrollment - data obtained at the Visit 8 of previous study D3820C00004) and Visit 4 (Week 12).

Urine drug screening tests and urinalysis will be performed on all patients at Visit 1 (enrollment - data obtained at the Visit 8 of previous study D3820C00004), Visit 4 (Week 12), and anytime during the study, at the discretion of the investigator, to allow appropriate

medical management of the patient. A urine pregnancy test for WOCBP will be performed at Visit 1 (enrollment - data obtained at the Visit 8 of previous study D3820C00004). If the urine pregnancy test is positive it is to be followed up with a serum pregnancy test. A serum pregnancy test for WOCBP will be performed at Visit 4 (Week 12) and Visit 5 (Week 14, follow-up).

For blood volume, see Section 7.1.

### 6.3.10.1 Urine drug screen

As noted above, urine drug screening tests will be performed on all patients at Visit 1 (enrollment - data obtained at the Visit 8 of previous study D3820C00004) and Visit 4 (Week 12), and anytime during the study, at the discretion of the investigator, to allow appropriate medical management of the patient. In addition, if, in the opinion of the investigator, a patient is undergoing opiate withdrawal or significant exacerbation of pain, the investigator is to conduct a urine drug screen to rule out non-compliance with the opioid regimen as an explanation for withdrawal or pain. Based on the results of the urine drug screen, clinical picture, and severity of the potential opiate withdrawal symptoms, the investigator will decide if the patient should be discontinued from the study. If the patient tests positive for other illicit drugs, it is up to the investigator to decide after consulting with the study physician, whether these drugs may compromise the patient's ability to comply with study instructions, and whether the patient should be continued in the study.

#### 6.3.10.2 Handling of subjects with elevated liver transaminases

The investigator will be alerted from the central laboratory regarding patients developing ALT or AST >3x ULN during the study, ie, all values above >3x ULN with no upper limit will be alerted. How to handle these patients is described in detail in this section.

All patients with ALT or AST >3x ULN, regardless of whether they stop or continue the intake of study drug, must be closely monitored with repeated laboratory liver tests every third day or more frequently if judged necessary by the investigator until the liver tests begin to improve. Thereafter, liver tests will be performed at an interval decided to be appropriate by the investigator. All patients must be followed until the liver tests have returned to baseline or until a firm explanation (diagnosis) for the elevated liver transaminases has been established.

The specific laboratory tests to be used for confirmation and monitoring include ALT, AST, alkaline phosphatase (ALP), bilirubin (BIL), conjugated BIL, INR, albumin, creatine kinase (CK), Hb, white blood cells (WBC), neutrophils, eosinophils, basophils, lymphocytes, monocytes, sodium, potassium, and creatinine.

#### Subjects who can continue the intake of study drug

• Patients with ALT or AST >3x ULN but ≤8x ULN and no clinical signs or symptoms indicating liver dysfunction can, at the discretion of the investigator, continue the intake of study drug with close monitoring.

The patients must be brought back to the study center for an unscheduled visit without any delay, but not later than 72 hours after the test results have been received, for specific evaluation of the underlying cause for the ALT or AST elevation and confirmatory laboratory testing.

A medical history focused on risk factors for liver injury (alcohol consumption, exposure to toxic agents, infections, medications and drug use including herbal remedies, etc) should be obtained, evaluation of recent symptoms (AEs), and physical examination should be done and all relevant information should be captured in appropriate eCRF modules.

Confirmatory laboratory testing should be done and more frequent monitoring of liver tests should be initiated.

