# **5.8 Discontinuation from study**

Patients are at any time free to discontinue from the study (IP and assessments), without prejudice to further treatment (withdrawal of consent). Such patients will always be asked about the reason(s) and the presence of any AEs. If possible, they will be seen and assessed by an investigator and Visit 4 assessments will be performed. Adverse events will be followed up (see Sections 6.3.4 and 6.3.5); and all study drugs should be returned by the patient.

Discontinued patients will not be replaced.

Patients should be discontinued in the following situations:

- Patient decision. The patient is at any time free to discontinue treatment, without prejudice to further treatment.
- Inadequate pain control after reasonable attempts to control pain have been unsuccessful
- Hepatotoxicity (significantly increased elevations in liver transaminases as defined in Section 6.3.10.2. The protocol for handling patients with elevated liver transaminases including guidelines for discontinuing patients is discussed in Section 6.3.10.2).
- Severe non-compliance to the CSP (including dosing regimen with NKTR-118 and/or prescribed opioid) as judged by the investigator in consultation with the study physician

- Incorrectly enrolled patients, involving increased safety risk. The investigator should consult with the study physician before discontinuing the patient unless there is a medical urgency.
- Patient is lost to follow-up
- The patient has a clinically significant or serious AE (eg, new or worsening heart failure) or sustained clinically significant treatment emergent abnormalities in vital signs that would not be consistent with continuation in the study, as determined by the investigator, AstraZeneca, or its representative, or the patient.
- Safety reasons as judged by the investigator
- Patient becomes pregnant
- Significantly worsened OIC refractory to medical treatment as judged by the investigator (including failure of the laxative rescue regimen)
- The patient is unable to comply with the restrictions on the use of concomitant medications as detailed in Section 5.6 (in such cases the investigator should consult with the study physician before discontinuing the patient).
- The patient is unable to tolerate the assigned dose of the study drug.

Abdominal pain has been reported as an AE in a previous trial with NKTR-118. The management of severe abdominal pain is discussed in Section 6.3.14.2.

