#### Subjects who stop intake of study drug

Patients with the following findings should immediately be contacted and instructed to stop intake of study drug:

- ALT or AST >8x ULN
- ALT or AST >5x ULN for more than 2 weeks
- ALT or AST >3x ULN AND (total bilirubin >2x ULN or INR >1.5). For further instructions on actions to be taken for patients meeting Hy's law criteria, see Appendix G.
- ALT or AST >3x ULN with the appearance of fatigue, nausea, vomiting, right upper quadrant pain or tenderness, fever, rash, and/or eosinophilia (>5%).

Patients must be brought back to the study center for an unscheduled visit without any delay, the next day if possible, but no later than within 72 hours after the test results have been received, for specific evaluation of the underlying cause of the ALT or AST elevation and confirmatory laboratory testing.

A medical history focused on risk factors for liver injury (alcohol consumption, exposure to toxic agents, infections, medications and drug use including herbal remedies, etc) should be obtained, evaluation of recent symptoms (AEs), and physical examination should be done and all relevant information should be captured in appropriate eCRF modules.

Confirmatory laboratory testing should be done and more frequent monitoring of liver tests should be initiated.

In addition, the following blood samples for differential diagnosis purposes should be taken in all patients who stop intake of study drug:

• Alcohol misuse: Carbohydrate deficient transferrin, S-ethanol

- Viral hepatitis: Immunoglobulin M antibody to hepatitis A virus (anti-HAV-IgM), Hepatitis B surface antigen (HBsAg), immunoglobulin M antibody to hepatitis B core antigen (anti-HBc-IgM), antibody to hepatits C virus (anti-HCV), hepatitis C virus ribonucleic acid (HCV RNA), immunoglobulin M antibody to Epstein Barr virus viral capsid antigen + immunoglobulin G antibody to Epstein Barr virus nuclear antigen (EBV VCA IgM + EBNA IgG), immunoglobulin M antibody to cytomegalovirus (anti-CMV-IgM).
- Autoimmune hepatitis: anti-nuclear antibody, anti-mitochondrial antibody, smooth muscle antibody, immunoglobulin G, immunoglobulin M, immunoglobulin A
- Hereditary disorders: S-Iron and total iron-binding capacity, S-Ferritin, ceruloplasmin, alpha 1-antitrypsin

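### Section 6.3.10.2 gives a permission to continue study drug that overlaps its own list of reasons to stop, and no text says how the two relate (minor internal contradiction)

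*Protocol*

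**What the plan says.** Section 6.3.10.2 of the protocol deals with transaminase elevations above 3x ULN in two consecutive subsections.

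The subsection on continuing first names the patients it covers: "Patients with ALT or AST >3x ULN but ≤8x ULN and no clinical signs or symptoms indicating liver dysfunction can". The rest of that sentence is what makes the rule a permission: "at the discretion of the investigator, continue the intake of study drug with close monitoring". The only conditions are the transaminase band and the absence of clinical signs or symptoms. Duration, bilirubin, INR and eosinophils are not mentioned, and neither is the stop list.

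The subsection on stopping opens with "Patients with the following findings should immediately be contacted and instructed to stop intake of study drug" and gives four findings:

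1. On level alone: "ALT or AST >8x ULN"
2. On level and duration: "ALT or AST >5x ULN for more than 2 weeks"
3. On level with a second laboratory result: "ALT or AST >3x ULN AND (total bilirubin >2x ULN or INR >1.5" (closing bracket omitted here)
4. On level with symptoms or eosinophils: "ALT or AST >3x ULN with the appearance of fatigue, nausea, vomiting, right upper quadrant pain or tenderness, fever, rash, and/or eosinophilia (>5" (the eosinophil limit is 5%; the quote stops before the percent sign)

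Section 5.8 lists hepatotoxicity among the reasons for discontinuation and refers back: "The protocol for handling patients with elevated liver transaminases including guidelines for discontinuing patients is discussed in Section 6.3.10.2".

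**The concern.** The continue band reaches up to 8x ULN, but three of the four stop findings start at 3x or 5x. A patient without symptoms can satisfy the permission to continue and also have a finding for which the next subsection directs an immediate stop. A safety stopping rule should give one instruction for each clinical picture.

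Three things could differ between sites that read the section differently:

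- **Dosing.** Whether study drug continues in a patient with persistent transaminase elevation, or with elevation plus abnormal bilirubin, INR or eosinophils.
- **Work-up.** The differential-diagnosis blood panel is required only in patients who stop.
- **Recording.** Under Section 6.3.4, being the reason for stopping study drug is one of the triggers for reporting a laboratory deterioration as an adverse event. Adverse events leading to discontinuation are among the safety variables in Section 6.3.1.

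**Working it through.** The plan gives no figure to reproduce. The check is whether the two sets of conditions intersect.

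Let x be ALT or AST as a multiple of ULN. All limits come from Section 6.3.10.2.

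- **Continue:** 3 < x ≤ 8 and no clinical signs or symptoms of liver dysfunction.
- **Stop 1:** x > 8.
- **Stop 2:** x > 5 for more than 2 weeks.
- **Stop 3:** x > 3 and (total bilirubin > 2x ULN or INR > 1.5).
- **Stop 4:** x > 3 and (a listed symptom and/or eosinophils > 5%).

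| Stop criterion | Region shared with the continue rule | Depends on reading? |
|---|---|---|
| 1 | None, since x cannot be both ≤ 8 and > 8 | No |
| 2 | 5 < x ≤ 8 for more than 2 weeks, symptom-free | No: overlaps on any reading |
| 3 | 3 < x ≤ 8 with bilirubin > 2x ULN or INR > 1.5, symptom-free | Yes: overlaps if laboratory values are not clinical signs |
| 4 | 3 < x ≤ 8 with eosinophils > 5% only, symptom-free | Yes: same condition |

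Illustrative profiles, with values chosen only to show the logic:

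- **ALT 6x ULN for 3 weeks, no symptoms.** 3 < 6 ≤ 8, so continuing is permitted. Also 6 > 5 and 21 days > 14 days, so criterion 2 directs a stop.
- **ALT 4x ULN with bilirubin 2.5x ULN, or with INR 1.6, no symptoms.** 3 < 4 ≤ 8, so continuing is permitted. Also 2.5 > 2, or 1.6 > 1.5, so criterion 3 directs a stop, given that these results are not clinical signs.
- **ALT 4x ULN with eosinophils 6%, no symptoms.** Continuing is permitted as above. Also 6 > 5, so criterion 4 directs a stop on the same condition.

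**Are laboratory values clinical signs?** Section 6.3.10.2 does not say. Section 6.3.2 lists symptoms, signs and abnormal investigation results as separate kinds of finding. Section 6.3.4 treats a laboratory deterioration as something that may or may not be accompanied by clinical signs and symptoms. That usage favours the reading under which criteria 3 and 4 overlap. Even if every laboratory abnormality were counted as a sign, the criterion 2 overlap would remain, because duration is not a sign.

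**Does other text set an order?** The opening of Section 6.3.10.2 speaks neutrally of patients who stop or continue. Section 5.8 sends the reader back to Section 6.3.10.2. Appendix G calls for an agreed follow-up approach when potential Hy's law criteria are met, and returns the reader to the protocol when they are not. None of these says that one list overrides the other.

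**How often can it arise?** Section 6.3.10 schedules serum chemistry at Visit 1 (taken from Visit 8 of the preceding study), Visit 4 (Day 85) and Visit 5 (Day 99). Dosing runs from Day 2 to Day 85, and unused drug is returned at Visit 4. No chemistry is scheduled in the 85 − 1 = 84 days between the first two samples. A decision to continue or stop during treatment would therefore come mainly from the enrollment sample or from unscheduled testing.

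**The case against.** The strongest reply is that the two rules differ in force. The continue rule is a permission left to the investigator; the stop rule is a direction. Stopping satisfies both, while continuing in the presence of a listed finding departs from the stop rule. A reader might infer that a site could do either and be equally compliant. The documents do not support that. Nor do they support reading the stop list as an absolute requirement, since the operative word is *should*.

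Section 5.8 also lends weight to the stop list. It makes hepatotoxicity, as defined in Section 6.3.10.2, a reason for discontinuation, and the four stop findings are the only discontinuation criteria there. No other section repeats the continue permission.

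The stop list does not exempt patients who are already continuing. Everyone above 3x ULN is retested at least every third day until the tests begin to improve, and the tests include bilirubin, INR and eosinophils. A criterion that requires more than 2 weeks presupposes a patient who was not stopped at once, which suggests a sequence and not two rival lists.

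A reader might also infer that the safety results would be distorted. That is not shown. Hepatotoxicity is not named among the areas of interest in Section 6.3.15, the safety variables refer only generally to adverse events leading to discontinuation, and the analysis is descriptive without testing.

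These points narrow the finding but do not remove it. Precedence for the stop list is a reasonable inference that the reader has to supply, because the continue paragraph is unqualified and no text states the order.

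**Conclusion.** The point holds as a minor internal contradiction. For symptom-free patients above 5x and up to 8x ULN for more than 2 weeks, Section 6.3.10.2 both permits continued dosing and directs a stop, however it is read. For patients above 3x and up to 8x ULN with the bilirubin, INR or eosinophil findings alone, it does so on the assumption that laboratory results are not clinical signs. The protocol's own usage favours that assumption but does not settle it. Three of the four stop criteria are involved, one unconditionally and two conditionally.

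The documents give no number of affected patients. Given the sparse chemistry schedule it is likely to be small. A patient in the continue band with none of the stop findings is not affected. No effect on the descriptive safety summaries has been demonstrated. No view is taken here on which instruction is clinically right.

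**What to change.** Reconcile the two subsections of Section 6.3.10.2 with one sentence in the continue paragraph. It should state how the permission relates to each of the four stop criteria, including the duration, bilirubin or INR, and eosinophil findings. It should also cover a patient who is continuing and later meets one of them, so that each pattern maps to a single instruction. The sponsor's medical team decides which instruction governs.

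The cost is one sentence in a protocol amendment and a memo to sites. No procedures, visits or patients are added.
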